9.7 Sensitivity Analyses

Sensitivity analyses will be conducted to examine if missing data or outliers significantly affected results. We will conduct sensitivity analysis for missing data by using pattern mixture models. The pattern of results will be compared to ITT analyses. Results will also be conducted after any outliers, defined as observations with values of greater than +3 or smaller than -3 z score units, are removed and compared to primary results.

9.8 Exploratory Subgroup Analyses

Pursuant to NIH guidelines on examining sex as a biological variable, we will examine if sex moderates any significant intervention effects identified in aim 1 or aim 2 analyses by examining sex x group x time interactions. Effect sizes will be reported by sex if there are any significant differences (alpha .05).

Relevant to aim 1 and 2 analyses, exploratory analyses will further examine effect size for the pre-to post-change of piano training relative to music listening instruction among those who were adherent (i.e., who completed 80% or more of assigned number of sessions) in both conditions. Analyses detailed above for specific aims 1 and 2 will be repeated among this subsample. Results and effects sizes among the adherent sample will be compared to the ITT derived results and effect sizes.

Relevant to aim 1 and 2 analyses, we will further examine if effects were moderated by a better ear pure-tone average (PTA). In these analyses we will examine if there are significant training group x time x hearing interactions on CAP, cognition, or everyday function, using an alpha of .05.

As it is possible that training will be differentially effective for those with CAP disorders (CAPD), we will identify a subgroup of participants (regardless of MCI status) who could be diagnosed with CAPD. Diagnosis of (C)APD requires performance deficits on the order of at least two standard deviations below the mean on two or more of the following tests^{39, 130}: temporal processing (TCS, ATTR), degraded speech understanding (WIN), or binaural processing (DDT, DST). Analyses for the cognition and everyday function outcomes will be repeated with groups defined as with/without CAPD as an independent variable. We will examine if there are significant training group x time x ADP status interactions using an alpha of .05.

We may also explore moderation effects of covariates such as MCI subtype (amnestic, non-amnestic, multiple domain) to determine who is most likely to benefit from the intervention among participants with MCI. To do so, we will examine three-way interactions (covariate x training group x time) stratified by MCI status, if MCI was a significant moderator in results of analyses for aim 2 described above. Effect sizes will be examined.

The self-efficacy measures (general self-efficacy and music performance self-efficacy) will be examined as exploratory outcomes by comparing the two randomized conditions across the two measurement points (before/after training). Analyses will include ordinal logistic regression analyses across levels of self-efficacy conducted within the generalized estimating equations (GEE) statistical framework to account for repeated measurements. Significant improvements on either measures demonstrated in this analyses will be followed by exploratory mediation analyses to examine if improvements in self-efficacy can account for any observed training

effects on CAP, cognition, or everyday function. Thus, we will examine an alternative hypothesis that training gains can be attributed to improved self-efficacy. An alpha of .05 will be used.

To explore if initial music aptitude affects performance within each of the training conditions, AMMA at baseline will be examined as a covariate (i.e., modifier) of Basic Piano Measure performance (BPM) from the first to the final day of training among those in the piano training condition. Similarly, baseline AMMA will be examined as a covariate on the Music Listening Measure (MLM) across the same two time points within the control group. Again, ordinal logistic regression with GEE will be used given the ordinal scaling of the outcomes. An alpha of .05 will be used.

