imately 3 seconds separate each sentence. Two 35-word lists are used; 5 words are presented at each of 7 signal-to-noise ratios (SNRs). The SNRs are presented in a decending manner, from 24 to 0 in 4-dB increments. The babble is maintained at a fixed level. Listeners must repeat the last word of the sentence, ignoring the babble. The WIN uses a modified method of constants to establish the SNR at which 50% correct performance is achieved on the materials. The 50% point is computed with the Spearman-Kärber equation^{98,99} [$50\% = 26 - (\#correct)(0.8)$; “.8” is the attenuation step size (4 dB) divided by the number of words per step (5)]. The WIN has been established as a reliable measure (intra-class correlation coefficient = 0.88)^{100,101}.

- **Dichotic Digits Test (DDT).** The DDT is a test of binaural processing that uses a closed set of stimuli (numbers), thus having a relatively low linguistic load. The DDT consists of numbers between one and nine, excluding the two-syllable number seven ($r=.79-.97$)¹⁰². Two numbers are presented to the right ear while two numbers are presented simultaneously to the left ear, for a total of four numbers. The talker is male. Approximately four seconds of silence separate each set of four numbers, and approximately one second separates the individual pairs within a set of four. The participants are instructed to repeat all four numbers that were presented to them, in any order. Twenty-five sets of four numbers each are presented, for a total of 100 stimuli. The test is scored as a percent correct out of the 100 numbers presented.

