- **Adaptive Tests of Temporal Resolution (ATTR).** The ATTR¹⁰⁵ is a copyrighted and freely downloadable test of auditory temporal processing. Details regarding the ATTR have been published previously¹⁰⁵⁻¹⁰⁷. Briefly, the ATTR is used to measure gap detection thresholds using a three-interval, two-alternative forced-choice adaptive procedure targeting 70.7% correct gap detection. The stimuli used to define the silent gaps are $\frac{1}{4}$ octave narrow bands of noise (NBN) centered on either 1 kHz or 2 kHz. Before the silent gap, the NBN is 300 ms in duration. After the silent gap, the NBN varies randomly in duration between 250 and 350 ms. The participant is presented with three intervals of sound, a reference interval, a standard interval identical to the reference interval, and a target interval. In the reference and standard intervals, two NBNs separated by a 1-ms gap are presented. In the target interval, two NBNs separated by a gap of adaptively varying duration are presented. The reference interval is presented first and the standard and target intervals are presented in random order, following the reference interval. The participant’s goal is to select the target interval from among the standard and target intervals. The participant is not allowed to select the reference interval. Two subtests of the ATTR were used in the present study, the within-channel subtest for which NBNs before and after the gap are both centered on 2 kHz and the across-channel subtest for which the NBN before the gap is centered on 2 kHz and the NBN after the gap is centered on 1 kHz. The ATTR was presented at a high, comfortable level, self-selected by each participant as described by Cox¹⁰⁸. Reliability for the ATTR has been established with intraclass $r = .58-.87$ ¹⁰⁵.

- Outcomes also include cognitive measures: Verbal Fluency Test (phonemic fluency, category fluency, and category switching), Trail Making Test, and Digit Coding

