9.2.1 Primary outcomes

- To examine the efficacy of piano training to improve CAP, cognition, and everyday function among older adults. We will assess the effects of piano training as compared to music listening instruction on CAP, cognition, and everyday function.

CAP includes Time Compressed Speech, Words-in-Noise, Dichotic Digits Test, Dichotic Sentence Identification and Adaptive Tests of Temporal Resolution. All are parametric tests of perception.

Cognition includes Verbal Fluency (phonemic, category, and switching), Digit Coding, and Trail Making test. All are parametric tests of cognitive function.

Everyday function includes the Timed IADL test and Test of Everyday Attention both parametric measures. Both measures will be examined individually.

Principal Component Analyses (PCA) will be performed with CAP, cognitive and functional measures to form composites of outcomes for use in analyses to reduce the number of comparisons.

Hypotheses: The piano training group will outperform the music listening instruction group on measures of CAP, cognition, and everyday function immediately post-intervention.

Secondary Objectives

The secondary objectives are:

- To examine the moderating effects of MCI on piano training efficacy. Moderating effects of MCI status will determine if piano training is effective for older adults with and/or without MCI. We do not have a directional hypothesis for this objective.
- To explore mediators of intervention effects.

Hypothesis: Grounded in theory⁸ and prior research⁹⁻¹¹, we hypothesize that piano training will improve CAP and cognitive performance, leading to functional improvements. We expect that enhanced CAP will mediate cognitive gains. We further hypothesize that cognitive gains will mediate functional improvements.

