Hearing	-0.09	0.06	.134	-0.14	0.06	.016
Visual acuity	-6.55	5.33	.220	-15.45	5.12	.003
Expectations	-0.79	0.67	.234	-1.96	0.64	.003
	Timed IADL+			Test of Everyday Attention		
Intercept	48.89	1.32	<.001	62.34	1.15	<.001

Group	3.15	2.67	.240	1.37	2.33	.557
Time	0.14	0.79	.863	-8.61	0.67	<.001
Group x time	-1.53	1.58	.327	-0.40	1.340	.765
Hearing	0.07	0.57	.194	-0.02	0.05	.603
Visual acuity	12.75	4.770	.008	0.24	4.470	.957
Expectations	1.02	0.59	.089	-0.79	0.56	.157

Note. ATTR=Adaptive Tests of Temporal Resolution, IADL=instrumental activities of daily living. MCI=mild cognitive impairment. +For ATTR and Timed IADL lower scores reflect better performance.

Table 14.3. *Effect sizes for piano training relative to music listening across composite outcomes and assessments for the analytic sample overall, among those adherent, and by cognitive status.*

Outcome Measure	d Effect Size			
	Overall (n =198)	Adherent (n =189)	Non-MCI (n =146)	MCI (n =52)
Central auditory processing composite	-0.01	-0.01	0.00	-0.07
Dichotic Digits	-0.06	-0.07	-0.03	-0.14
Dichotic Sentence Identification	0.01	0.01	0.02	-0.07
Time Compressed Speech	-0.01	0.01	0.03	-0.06
Words in noise	0.03	0.03	0.12	0.01
Adaptive Tests of Temporal Resolution composite	0.17	0.20	-0.09	0.24
Cognitive composite	-0.03	-0.03	-0.10	0.08
Trails A	0.03	0.06	0.00	0.43
Trails B	-0.17	-0.20	0.01	-0.54
Digit Symbol Coding	0.08	0.09	0.06	0.26
Test of Everyday Attention - Visual elevator timing subtest	0.02	0.02	0.03	0.44
Test of Everyday Attention - Telephone search time	-0.29	-0.32	0.08	-0.27
Verbal fluency composite	0.05	0.06	0.09	-0.12

Letter fluency	0.00	0.02	0.09	-0.36
Category fluency	0.18	0.20	0.18	0.13
Switching fluency	-0.06	-0.05	-0.07	-0.05
Test of Everyday Attention composite	0.04	0.08	-0.30	-0.02
Visual Elevator accuracy	0.01	0.03	-0.12	-0.19
Dual task decrement	0.10	0.13	-0.18	0.22
Timed Instrumental Activities of Daily Living composite	-0.15	-0.21	0.09	-0.13

Note. MCI=mild cognitive impairment. *d* effect sizes were calculated as pre- to post- change in the piano training condition relative to the music listening condition divided by the baseline standard deviation such that positive values would indicate improvement. Adherent analyses include those who completed 15 or more sessions of the assigned condition.

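### Section 9.8 tests moderation by central auditory processing disorder (CAPD) only through a two-SD cut-off. A continuous baseline CAP score should carry this exploratory test.

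*Combined protocol and SAP*

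**What the plan says.** Section 9.8 sets out to find participants, whatever their MCI status, who might meet a diagnosis of CAPD. The criterion is "performance deficits on the order of at least two standard deviations below the mean on two or more of the following tests". The list of tests reads "temporal processing (TCS, ATTR), degraded speech understanding (WIN), or binaural processing (DDT, DST" (closing bracket left off here). The cognition and everyday function analyses are then repeated with CAPD status as a factor, testing group by time by status at alpha .05. The section gives no expected count and no power, does not say whose mean applies, and plans no continuous version.

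Other sections bear on this:

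- Section 9.2.1 gives the CAP tests as "Time Compressed Speech, Words-in-Noise, Dichotic Digits Test, Dichotic Sentence Identification and Adaptive Tests of Temporal Resolution". There is no DST among them.
- Section 6.3.5 describes WIN as a method "to establish the SNR at which 50% correct performance is achieved on the materials", scored as 26 minus 0.8 times the number correct, and says "the ATTR is used to measure gap detection thresholds". ATTR has two subtests. The note to Table 14.2 adds: "For ATTR and Timed IADL lower scores reflect better performance".
- Section 9.6 builds standardised baseline composites that allow for score direction. Its MCI rule names age, sex and education norms.
- Section 5.5 stratifies randomization by MCI status only.

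**The concern.** CAP is the mechanism the trial proposes, so whether people with poor CAP respond differently is a sensible exploratory question. A cut at two SD on two tests discards most of the information in the scores and sets a small group against everyone else. The precision of such an interaction is governed by the smaller group. CAPD is not a stratum, so a handful of cases may also split unevenly between arms. A null result could then be read as evidence that baseline CAP does not matter, when the test could hardly have shown otherwise. How small the group is depends on a reference mean that the plan does not name.

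**Working it through.** **Inputs from the documents.** N = 198 is the minimum in Section 9.3 and the overall n in Table 14.3. The rule is two or more of five tests at two SD. Alpha is .05.

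**Assumptions, not in the documents.** Scores are normal, equally correlated at r = .3, .5 or .7, with ATTR counted once and DSI read for DST. Pre-post correlation is .7.

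**The plan's own figure.** Section 9.8 gives no power, but Section 9.3 gives 95% for Aim 1 at N = 198 and f = 0.10. With lambda = f² × N × 2/(1 − rho):
- rho = .7: lambda = 0.01 × 198 × 2/0.3 = 13.2, power 95.1%.
- rho = .5: lambda = 7.92, power 80%.

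So the stated figure implies a pre-post correlation of .7, which I use below. The SD of change is then √(2 × (1 − .7)) = 0.775 baseline SD.

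**Step 1: how many people qualify.** I simulated 1,000,000 records per correlation, with deficits taken as poor performance, and multiplied the proportion by 198. The last two columns are explained in step 3. Entries are for r = .3 / .5 / .7.

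| Reference | CAPD cases of 198 | Power, 0.5 SD of change | CAP gap, CAPD vs rest (SD) | Power of category if slope is 0.31 |
|---|---|---|---|---|
| Sample mean | 2.9 / 4.2 / 5.2 | 7 / 8 / 9% | 2.3 / 2.3 / 2.3 | 12 / 16 / 18% |
| Norm, sample 0.5 SD worse | 13 / 15 / 17 | 14 / 16 / 16% | 1.9 / 1.9 / 2.0 | 26 / 30 / 33% |
| Norm, sample 1.0 SD worse | 41 / 42 / 41 | 30 / 30 / 30% | 1.6 / 1.7 / 1.7 | 44 / 47 / 49% |
| Norm, sample 1.5 SD worse | 89 / 84 / 79 | 42 / 41 / 41% | 1.5 / 1.5 / 1.6 | 54 / 56 / 58% |

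On the sample mean the count is about 1 to 12 over N of 198 to 360, five or six scores and correlations of 0 to .8. It is about 7 to 11 at N = 198 if scores are skewed towards poor performance.

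**Step 2: power of the interaction.** With c cases split evenly by arm, SE = √(4/c + 4/(198 − c)) in SD of change.
- c = 4: SE = √(1 + 0.0206) = 1.01. Detectable at 80% power: 2.80 × 1.01 = 2.83 SD of change, or 2.83 × 0.775 = 2.19 baseline SD. Power for 0.5 is 8%.
- c = 10: power 12%.
- c = 40: SE = 0.354; detectable 0.99; power 29%.
- c = 87: SE = 0.286; detectable 0.80 (0.62 baseline SD); power 42%.

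An interaction of 0.5 SD of change is 0.5 × 0.775 = 0.39 baseline SD. That exceeds the d = 0.25 that Section 9.5 uses as its interim benchmark for the training effect itself. With 4 cases, the chance that one arm has one or none is 2 × (1 + 4)/16 = 0.63.

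**Step 3: continuous moderator, in the same units.** SE of the slope = 0.775 × 2/√198 = 0.110, so the detectable slope is 2.80 × 0.110 = 0.31 baseline SD per SD of CAP. With a pre-post correlation of .5 it is 2.80 × 2/√198 = 0.40.

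A slope per SD and a contrast between groups are different quantities, so I converted one to the other. If the true slope is 0.31, the category contrast is 0.31 times the CAP gap. On the sample mean with r = .5 that is 0.31 × 2.33 = 0.72 baseline SD. Its SE is 0.775 × √(4/4.2 + 4/193.8) = 0.76, giving power of about 16%. Across the table the category has 12% to 58% power where the continuous score has 80%. This step uses the mean of all five tests as the CAP score. Section 14 keeps ATTR as a separate composite, so the figures are approximate.

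**The case against.** Much can be said for the plan. The analysis is labelled exploratory and serves no primary or secondary objective. Its diagnostic wording may well point to published norms, under which the group could be sizeable. A diagnostic category also answers a question that clinicians ask, which a slope does not, and the slope needs moderation to be roughly linear. All of this stands. It limits the point to a minor one and is why the category should stay as a description.

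Three stronger readings are tempting and are not supported.

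- **The rule flags good scorers.** WIN and ATTR run lower-is-better, so a reader might infer that two SD below the mean picks out the best performers. The text asks for performance deficits, and Section 9.6 shows that the authors handle direction. Even on a literal reading with raw scores, about 0.5 to 1.5 people of 198 would be wrongly flagged.
- **The trial relies on a test it does not give.** DST appears only in this paragraph, and DSI is the second dichotic test everywhere else. It is a clerical slip.
- **The analysis cannot answer its question because only 3 to 5 people qualify.** That count needs the sample mean, N = 198, five normal scores and assumed correlations. The plan does not choose the sample mean.

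**Conclusion.** The concern holds as a point about the choice of moderator. The dichotomy is a weak way to ask whether baseline CAP changes the training effect, whichever reference is used: power for 0.5 SD of change runs from about 7% to 42% over the counts considered. For the same linear moderation, the continuous score always does better. The counts rest on assumed correlations and normality, the comparison on linear moderation and a pre-post correlation of .7. The unnamed reference, the unstated direction, DST and the ATTR count are details to tidy. None of them alone would justify the point. Severity is minor. Section 14 as given reports no CAPD result, and nothing here touches the primary conclusion.

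**What to change.** In Section 9.8, add training group by time by continuous baseline CAP composite, for cognition and everyday function, as the main exploratory test of whether baseline CAP moderates the effect. Add the same term for the ATTR composite, reverse-scored so that higher is better. The existing ATTR score cannot be used unchanged, because lower is better on it.

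Keep CAPD as a secondary descriptive category and report its count per arm. Name the reference norm. Define a deficit as worse performance: low for TCS, DDT and DSI, high for WIN and ATTR. Replace DST with DSI, and count ATTR once.

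The cost is a few sentences in the plan and a small set of exploratory models on data already collected. The downside is that the main result becomes a slope rather than an effect in a diagnostic group, and that it assumes roughly linear moderation.

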10 DATA COLLECTION, SITE MONITORING, AND ADVERSE EXPERIENCE REPORTING

10.1 Records to Be Kept

A visit control sheet (VCS) will be the only document indicating the participants name and subject id. This data form will be kept in a locked filing cabinet separate from the study data. This data form will be accessible to the Testers and Trainers as well as PIs, only.

Signed consent forms will be kept in locked filing cabinets separate from the data forms and will not contain the subject id number.

We will keep all completed telephone screening interviews to track the number of screenings completed, number scheduled, and reasons ineligible. We will keep the data forms completed and intervention records, which will contain subject id only, in a locked filing cabinet.

All documents will be kept for at least 5 years post-study close out (or longer if required by site IRB or NIH or other governing body).

The study database will not include participant names or other identifying information. When the study data are released for sharing, the data will be completely de-identified with any potentially identifying information (e.g., date of birth) removed.

10.2 Data Management

10.2.1 Clinical site responsibilities in data collection and management.

Each study participant will have a folder with participant id for all assessments completed for each study visit and for the intervention phase. Every data form (page) will include the participant id and date the form was administered.

Original versions of the data forms arranged by study visit will be kept in a locked filing cabinet in the lab noted with an electronic file location in the footer. Data forms will only be copied from these originals only. Each testing visit will include a detailed checklist of all measures to be administered and procedures to be followed, which will be initialed by the tester upon completion.

Immediately after completing a participant visit, the tester will score the assessments and check all forms for completion, and within 21 days a different tester should use a detailed checklist to review all of the data forms for accuracy and completion. Any unclear or missing items are queried to the Tester or study participant as appropriate. This quality control process helps to avoid missing data. This process will be repeated as necessary prior to data entry until the checklist is completed. This rescoring process is the first step of our data quality control process.

At the end of each testing visit and intervention phase, every data form will be reviewed in a five-step quality control audit (scoring, rescoring, entry, checking, reconciling) with each subsequent step performed by a different Research Assistant.

The data will be entered into a custom-designed MS Access database that uses MS SQL Server as the back end relational database and completely integrates study management (e.g., create forms, collect data, generate reports, prepare for analysis). The database is designed to ensure access control, audit control, data integrity, user authentication, and transmission security. The data quality control and custom database function to minimize missing data and ensure data integrity.

Only individuals trained by the PI or Study Coordinator to use the MS Access database will enter data. Reports reflecting entered data will be printed for each testing visit of each participant upon data entry. The data report will be checked for accuracy with the raw data by a trained staff member other than who entered the data. Errors or omissions will be returned for reconciliation and the process will be repeated until the entered data are deemed error free. Additionally, a random audit of 20% of folders entered will be completed each replicate.

11 Quality Assurance

The study protocol including a priori hypotheses and data analytic plan will be published online within 90 days of commencement of data collection. Any changes to the protocol or analytic plans will be documented with date of change and justification.

All study staff who recruit, interview, or assess study participants will be required to attend a weekly staff meeting with the Principal Investigator throughout the data collection phase of the study. Recruitment goals and procedures will be reviewed. Problems or issues will be discussed and resolved. Detailed minutes of the meetings proceedings will be kept for review by any personnel who are on vacation or ill and miss a meeting. If staff change, new personnel will review all previous study meeting minutes prior to working on the project. The study coordinator will keep these records from each staff meeting.

The study investigators will meet about monthly during the first quarter of the study, will meet at interim analyses, and at least annually to review/monitor any adverse events, if they occur. The study investigators may also meet monthly in the final quarter of the study to complete data analysis, interpretation, and publication.

All study staff will read, be instructed in, and may be asked to pass a certification exam on the study protocol before working on assigned study activities. All study staff will be required to complete IRB Human Subjects training prior to working on the project with re-certification completed as required by the NIH or IRB. This will be monitored and implemented by the study coordinator.

Telephone screeners will be required to complete two practice interviews with the first actual study interview supervised and evaluated by the Principal Investigator, Study Coordinator, or trained and certified telephone screener. The Study coordinator or other site personnel appointed to do will audit the first telephone screening interview completed and will continue to do so until the questionnaire and final outcome are completed without error.

The Testers, who will administer the baseline, clinical and post-test visits, will be required to practice administration of all study measures per the study protocol with three persons. The testing must be completed with at least two individuals who meet the study age requirements. The third practice visit will be supervised by the Principal Investigator, Clinical Coordinator, or a trained and certified tester (more practice may be deemed necessary by the observer). The first actual study assessment visit will also be supervised and evaluated by one of these study personnel. To further achieve internal validity and inter-rater reliability, the testers will observe and evaluate each other at least once per replicate and audit each other's testing records. Participant data forms should be audited by a different tester within 21 days of completion per a detailed rescoring checklist. Any missing, incomplete, or unclear items will be queried to the tester or participant as appropriate. The Study Coordinator will implement and monitor this process. Additional training and certification is required to administer the Clinical Dementia Rating Scale.

A detailed intervention protocol will be developed for Trainers. The Trainers may be required to pass a certification test of the intervention protocol prior to interacting with study participants during the intervention phase. The Trainers will be required to complete at least 5 hours of training activities that they will administer as a part of their training, prior to administering the intervention exercises to actual study participants. They will complete an initial mock training session under the observation of the PI, Study Coordinator, or another trained Research Assistant Trainer prior to conducting an actual study intervention visit. To further achieve internal validity and intervention fidelity, the trainers will observe and evaluate each other at least once per replicate and audit each other's intervention records. The first actual intervention visit conducted by the trainer will also be supervised and evaluated by the study coordinator or a certified trainer. Participant training data forms will be audited by a different trainer within 21 days of completion per a detailed rescoring checklist. Any missing, incomplete, or unclear items will be queried to the trainer or participant as appropriate. The Study Coordinator will implement and monitor this process.

The Study coordinator or other site personnel appointed to do so will audit the first testing/intervention folder completed and rescored by each tester/trainer, and will continue to do so until the procedure is completed without error. Random quality control audits will be performed on 20% of the participant folders each replicate.

Study documents and pertinent records will be available for inspection by monitoring authorities (e.g., NIH or IRB) as requested.

